### 9.5.2 Analyses of Secondary Efficacy Endpoint(s)

For the secondary endpoints, the missing data of the binary response parameters will be imputed using the non-responder imputation (NRI) and MI, as appropriate. The binary responses in the Placebo-controlled Phase will be analyzed using the CMH method, adjusted for use of glucocorticosteroids at baseline (yes/no) and use of a csDMARD (naïve, prior use only, or prior and concomitant use).

A mixed-effect model of repeated measures (MMRM) will be used to analyze the continuous endpoints. Because of the nature of the MMRM method, data from all timepoints during the Placebo-controlled Phase will be included in the model. Data obtained after early escape for subjects who escape early at Week 16 will be set to missing. Change from baseline will be analyzed using the MMRM approach with treatment group, time, treatment-by-time interaction, use of glucocorticosteroids (yes/no), use of csDMARD (naïve, prior use only, or prior and concomitant use) as factors, and baseline value as a covariate. Time will be treated as a categorical variable in the MMRM model. An unstructured covariance matrix will be used to model the within subject covariance. If the MMRM model using an unstructured covariance matrix fails to converge with the default Newton-Raphson algorithm, the Fisher scoring algorithm or other appropriate methods can be used to provide initial values of the covariance parameters. In the rare event that none of the above methods yields convergence, a structured covariance such as heterogeneous Toeplitz and Toeplitz structures will be used to model the correlation among repeated measurements. In this case, the empirical option will be used because the sandwich variance-covariance estimator is asymptotically consistent. Within-group least-squares (LS) mean changes from baseline, the associated standard errors (SEs) and 2-sided 95% Cls, treatment differences in LS mean changes from baseline at Week 16 and the associated 2-sided 95% CIs and 2-

[figure not shown]
Page 51 of 67

Protocol Number: 20200058
Date: 07 February 2023
Page 52 of 67

sided p-values will be obtained from the MMRM model and will be provided in the summary table.

All analyses on endpoints including joint counts will be performed on those joints that are affected at baseline (defined as sentinel joints).

9.5.3 Analyses of Exploratory Efficacy Endpoint(s)

Protocol Number: 20200058 Date: 07 February 2023

Page 53 of 67

Protocol Number: 20200058

Date: 07 February 2023

Page 54 of 67

#### 9.6 Safety Analyses

#### 9.6.1 Analyses of Primary Safety Endpoint

Safety will be evaluated via descriptive statistics and point estimates. Unless otherwise specified, all safety analyses described in this section will be performed for both the Placebo-controlled and Apremilast-exposure Phases (Section 5.5).

Safety analyses for the Placebo-controlled Phase will be based on the safety population and presented by treatment group (apremilast 30 mg BID and placebo); the data included are up to Week 16/Visit 5 for placebo-treated subjects who early escape and up to Week 24/Visit 6 for all other subjects. For the Apremilast-exposure Period, the analyses will be based on the apremilast subjects as treated population and include data from Day 1 of apremilast exposure, irrespective of when the apremilast exposure starts (at Week 0, 16, or 24). For both the Placebo-controlled Phase and the Apremilast-exposure Period, the data included will be up to 28 days after the last dose of IP or the date of death (if applicable), whichever comes first, for subjects who discontinue prematurely.

For the analyses of AEs and marked abnormalities, the following point estimates are provided, unless otherwise specified:

 Subject incidence: Subject incidence (i.e., percentage [%] used in a frequency summary) is defined as the number of subjects with the specific event divided by the number of subjects included in the analysis, multiplied by 100. Subjects with multiple occurrences of a specific event in a defined exposure interval will be counted only once in the numerator.

Protocol Number: 20200058

Date: 07 February 2023

Page 55 of 67

• Exposure-adjusted incidence rate (EAIR) per 100 subject-years: The EAIR per 100 subject-years is defined as 100 times the number of subjects with the specific event divided by the total exposure time (in years) among subjects included in the analysis. Subjects with multiple occurrences of the specific event in a defined exposure interval will be counted only once in the numerator. The EAIR per 100 subject-years is interpreted as the expected number of subjects with at least one occurrence of the specific event per 100 subject-years of exposure to the IP.

Total exposure time: The total exposure time in years is calculated by dividing the sum of exposure time in days over all subjects included in the analysis by 365.25 days. The exposure time for a subject without the specific event is the treatment duration, whereas the exposure time for a subject with the specific event is the treatment duration up to the start date (inclusive) of the first occurrence of the specific event. If the subject experiences an event which starts on the first dose of the phase/period, the exposure time of that subject for that event is 1 day.

In summaries of continuous variables with summary statistics by time point, values for baseline, time point, and change from baseline will be summarized at each time point for subjects who have values at both baseline and the specific post-baseline time point. Frequency summaries of shifts from baseline to post-baseline time points will be provided for subjects who have values at both baseline and each individual specific post-baseline time point. In addition to the scheduled visits, shift summaries will also be provided from baseline to the end of phase/period and to the worst value, including scheduled and unscheduled visits, in a specific post-baseline phase/period.

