Week 24, n (%)	12 (11.0)	22 (20.0)	
ACR 70			
Week 16, n (%)	0 (0.0)	7 (6.4)*	
Week 24, n (%)	5 (4.6)	8 (7.3)	

ACR 20/50/70 = American College of Rheumatology 20%/50%/70%; APR = apremilast; BID = twice daily; FAS = Full Analysis Set; NRI = nonresponder imputation.

Note: **p < 0.01 for apremilast versus placebo..*p < 0.05 for apremilast versus placebo.

Table 6: HAQ-DI Score (0 to 3) Change From Baseline at Weeks 16 and 24 (FAS; MMRM)

Visit		Change From Baseline
Treatment Group	n ^a	LS Mean (SE) ^b
Week 16		
Placebo	109	-0.055 (0.0513)
APR 30 BID	109	-0.205 (0.0523)*
Week 24		
Placebo	109	-0.169 (0.0581)
APR 30 BID	109	-0.273 (0.0572)

APR = apremilast; BID = twice daily; DMARD = disease-modifying antirheumatic drug; EE = early escape; FAS = full analysis set; HAQ-DI = Health Assessment Questionnaire – Disability Index; LS = least-squares; MMRM = mixed-effects model of repeated measures; SE = standard error.

^a Subjects with a baseline value and at least 1 postbaseline value (after exclusion of data for EE subjects) during the Placebo-controlled Phase are included in the MMRM analysis. n with non-missing values were 103 and 91 for Placebo and APR 30 BID at Week 16, and 63 and 76 at Week 24, respectively.

b The LS mean (SE) and 2-sided p-value are based on an MMRM analysis for the change from baseline, with treatment group, time, treatment-by-time interaction, and previous DMARD use and baseline oral corticosteroids (prednisone or equivalent) use as factors and the baseline value as a covariate. An unstructured covariance matrix that is homogeneous across treatment groups was used. The p-values in italics are < 0.05 and are considered nominally significant, as hierarchical testing was stopped after the first secondary endpoint.

Protocol CC-10004-PSA-013

Among patients with enthesitis at Baseline, significant improvements from Baseline in Gladman Enthesitis Index (GEI) score were observed with APR 30 mg (-1.1) vs placebo (-0.4) at Week 2 (P=.0354), as well as at Weeks 16 and 24 (Table 7).

In addition, numerically greater proportions of subjects treated with APR 30 mg (48.2%) compared to placebo (33.3%) achieved GEI scores of 0 at Week 24.

Table 7: Gladman Enthesitis Index Change From Baseline at Weeks 16 and 24 During the Placebo-Controlled Period in Subjects With Pre-existing Enthesopathy (FAS; MMRM)

		Change From Baseline		
Visit Treatment Group	n ^a	Week 16 LS Mean (SE) ^b	Week 24 LS Mean (SE) ^b	
Placebo	51	-0.4 (0.26)	-0.5 (0.27)	

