6.5.5. Diarrhea, Nausea and Vomiting

Apremilast has been associated with AE reports of diarrhea in clinical trials. Most diarrhea events were of mild or moderate severity and reported within the first 2 weeks of treatment, usually resolving within 4 weeks without medical intervention.

Diarrhea is the passage of three or more loose or liquid stools per day, or more frequently than is normal for the individual (World Health Organization [WHO], 2013). Following the definition of diarrhea by the WHO and taking a more conservative approach, the AE of diarrhea in this protocol is defined as having two or more watery/liquid stools in a day.

To better characterize diarrhea and to distinguish similar events coding to the Medical Dictionary of Regulatory Activities (MedDRA) preferred term of diarrhea, subjects reporting diarrhea or similar events (eg, frequent bowel movements, loose bowels, etc.) will be asked whether they have had two or more watery/liquid stools in a day. Subjects who respond "yes" to this question will be further asked how often, on average, have they experienced two or more watery/liquid stools in a day. Subjects who respond "no" to the question will not be asked any further questions. This data will be reported via electronic data capture in the ERT tablet. If an AE is identified by the Investigator, the AE and respective attributes will be reported in the clinical database. If the AE meets serious criteria, it must be reported to Amgen Global Patient Safety (see Section 10.5).

There have been post-marketing reports of severe diarrhea, nausea, and vomiting associated with the use of apremilast. Most events occurred within the first few weeks of treatment. In some cases, patients were hospitalized.

Subjects 65 years of age or older and subjects taking medications that can lead to volume depletion or hypotension may be at a higher risk of complications. Subjects should be monitored for the occurrence of severe diarrhea, nausea and vomiting. If a subject develops severe diarrhea, nausea and vomiting, discontinuation of study treatment may be necessary (see Section 11).

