## 3. Study Overview

#### 3.1 Study Design

This Phase 4 multicenter, randomized, placebo-controlled, double-blind study is designed to evaluate the efficacy, safety and tolerability of apremilast over 48 weeks of treatment in approximately 285 subjects with early oligoarticular psoriatic arthritis.

Protocol Number: 20200058

Date: 07 February 2023

Page 18 of 67

subjects will be randomized in a 2:1 ratio to either apremilast 30 mg BID or identically appearing placebo via an Interactive Web Response System (IWRS).

Randomization to apremilast arm or placebo arm will be stratified by concomitant use of glucocorticosteroids at baseline (yes/no) and prior/concomitant use of a csDMARD, either MTX or SSZ, (i.e., csDMARD-naïve; csDMARD use prior to baseline [treatment not continued]; or csDMARD use prior to and concomitant at baseline). The number of subjects who are csDMARD-naïve is targeted to comprise up to 50 % of the subjects enrolled in the study. There is no planned protocol extension following the end of the study.

This is a 56-week study which will consist of 4 phases:

- Screening Phase up to 4 weeks
- (Randomized, Double-blind) Placebo-controlled (Treatment) Phase Weeks 0 to 24.
  - Stratified randomization (2:1 ratio to either apremilast 30 mg BID or placebo).
  - Dose-titrated.
  - Subjects with no improvement in SJC (based on sentinel joints, i.e., the joints affected at baseline) at Week 16 are eligible for Early Escape (EE), at the discretion of the Investigator; Placebo-treated subjects who escape early will be transitioned to apremilast 30 mg BID in a blinded fashion via IWRS, while apremilast-treated subjects will remain on the original treatment assigned at baseline.
  - The patients remaining on placebo will be transitioned to apremilast 30 mg BID at Week 24.
  - All subjects who complete this 24-week treatment phase will have the option to enter the Active-treatment Extension Phase.
- (Active-treatment) Extension Phase Week 24 to Week 48.
  - Beginning at Week 24 Visit, all subjects in the Extension Phase will be dispensed open-label apremilast (30 mg BID).
  - All subjects will receive apremilast 30 mg BID until the completion of the study (i.e., up to Week 48 Visit)
- (Post-treatment) Observational Follow-up Phase up to 4 weeks.

[figure not shown]

Protocol Number: 20200058
Date: 07 February 2023
Page 19 of 67

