#### 5.5 Analysis Phases/Period

For the purposes of data analysis and reporting, below analysis phases/period for post-baseline data are defined: the Placebo-controlled Phases (through Week 24 and through Week 16) and the Apremilast-exposure Period.

The start and stop dates of each analysis phases/period are defined below, unless otherwise defined for a specific analysis or summary. Analyses for a specific period will include all data occurring, measured or collected (based on date of occurrence or measurement, or date of specimen collection, as appropriate) between the start and stop dates (inclusive or exclusive, depending on the data type) of that analysis phases/period. The specific rules for including or excluding the start and stop dates, depending on the data type, are also given below.

- Placebo-controlled Phase through Week 24:
  - Start date: The date of the first dose of IP.
  - Stop date:
    - The date of the first Week 16/Visit 5 dose for placebo-treated subjects who escape early at Week 16/Visit 5 and take at least one dose of IP dispensed at that visit, or
    - The date of the first Week 24/Visit 6 dose for subjects who complete Week 24/Visit 6, except for placebo-treated subjects who escape early, or
    - For all other subjects (i.e., subjects who discontinue prior to Week 24/Visit 6, with the exception of placebo-treated subjects who discontinue after early escape and has taken at least one dose of IP dispensed at Week 16/Visit 5), the date of the last study visit (including the Early Termination Visit and the Observational Follow-up Visit; i.e., all data after the start date will be included) for efficacy analyses, or 28 days after the last dose of IP or the date of death (if applicable), whichever comes first, for safety analyses.

Protocol Number: 20200058
Date: 07 February 2023
Page 33 of 67

Placebo-controlled Phase through Week 16:

- Start date: The date of the first dose of IP.

Stop date:

- The date of the first Week 16/Visit 5 dose for placebo-treated subjects who escape early at Week 16/Visit 5 and take at least one dose of IP dispensed at that visit, or
- The last non-missing Week 16/Visit 5 date for subjects who complete Week 16/Visit 5, except for placebo-treated subjects who escape early, or

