## 7.2 Primary Analysis

After all subjects have completed the Week 24 Visit (or discontinued from the study), a Week 24 database restriction will be performed, the primary data analysis will be conducted. However, unblinded data will only be made available to selected Sponsor and Contract Research Organization (CRO) team members involved with analysis of the data. All other Sponsor, site, and CRO personnel directly involved with the conduct of the study, will remain blinded to treatment assignments until the final database lock at the conclusion of the study.

The primary analysis will present data from the completed placebo-controlled phase of the study, including the primary, secondary endpoints at Week 16, and and safety results up to week 24.

Page 35 of 67

Protocol Number: 20200058
Date: 07 February 2023
Page 36 of 67

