
New events of all TEAEs by exposure interval will be summarized for the Placebo-controlled Phase ( $\leq 1$ , > 1 to  $\leq 4$ , > 4 to  $\leq 8$ , > 8 to  $\leq 12$ , > 12 weeks) and the Apremilast-exposure Period ( $\leq 1$ , > 1 to  $\leq 4$ , > 4 to  $\leq 8$ , > 8 to  $\leq 12$ , > 12 to  $\leq 16$ , > 16 to  $\leq 28$ , > 28 to  $\leq 40$ , > 40 weeks). An event with a start date falling into an exposure interval is considered a new event for that interval. Each subject is counted once in the numerator of a subject incidence for each applicable specific TEAE in each exposure interval where an event started. The denominator of a subject incidence is the number of subjects with treatment duration exceeding the lower bound of the particular exposure interval.

All TEAEs will be summarized by age, sex, glucocorticosteroid use at baseline and prior/concomitant use of csDMARD. Subgroups of glucocorticosteroid use at baseline and prior/concomitant use of csDMARD will be based on the actual data, not by the data from IWRS.

If there are deaths, a listing will be provided.

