#### 9.6.9 Exposure to Investigational Product

Descriptive statistics will be produced to describe the exposure to investigational product by treatment group. Compliance to each IP will also be summarized.

Page 59 of 67

Protocol Number: 20200058 Date: 07 February 2023

Treatment duration will be summarized by treatment group for the Placebo-controlled Phase using the safety population.

Summary statistics for treatment duration (in weeks), as well as a frequency summary of treatment duration categories (e.g., < 4,  $\ge 4$  - < 8 weeks, etc.) and exposure categories (e.g.,  $\ge 1$  day,  $\ge 4$ ,  $\ge 8$  weeks, etc.), will be provided.

Treatment duration (in weeks) is calculated as (the date of the last dose of IP – the date of the first dose of IP + 1) / 7 and rounded to one decimal place.

When partially missing last dose date is available, set last dose date to the maximum of [the earliest possible date given the non-missing field(s) of last dose date, the minimum of (the latest possible date given the non-missing field(s) of last dose date, last known date in database, first non-missing Early Termination (ET) visit date)].

When the last dose date is completely missing, set the last dose date to the minimum of (the last known date in database, first non-missing Early Termination (ET) visit date).

Last known date in database is defined as maximum of (last visit date, clinical efficacy assessment date, lab, vital signs, AE start or end dates, concomitant medications start or end dates, concomitant procedure date, treatment exposure start date or end date where doses were completely or partially taken, death date).

The specific definitions of the first and last dose dates for the Placebo-controlled Phase and Apremilast-exposure Period are given below:

- Placebo-controlled Phase:
  - First dose date: The date of the first dose of IP.
  - Last dose date:
    - the date prior to Week 16/Visit 5 for placebo-treated subjects who escape early at Week 16/Visit 5 and take at least one dose of IP dispensed at that visit, or
    - the date prior to Week 24/Visit 6 for subjects who complete Week 24/Visit
       6 dose, except for placebo-treated subjects who escape early
    - For all other subjects (i.e., subjects who discontinue prior to Week 24/Visit 6), the date of the last dose of IP in the study.

Page 60 of 67

Protocol Number: 20200058 Date: 07 February 2023

e: 07 February 2023 Page 61 of 67

- Apremilast-exposure Period:
  - First dose date:

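### The new-onset adverse-event table ends in an open interval beyond 12 weeks, where placebo escapers have about 4 weeks at risk and other Week 24 completers about 12

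*SAP*

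**What the plan says.** Early escape at Week 16 is open to subjects in either arm who meet the criterion. Placebo escapers are switched, while "apremilast-treated subjects will remain on the original treatment assigned at baseline" (SAP 3.1).

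The safety cut-off follows the change of drug. SAP 9.6.1 includes Placebo-controlled Phase data "up to Week 16/Visit 5 for placebo-treated subjects who early escape and up to Week 24/Visit 6 for all other subjects". SAP 5.5 gives the same rule for the phase through Week 24, with the stop date for completers being "The date of the first Week 24/Visit 6 dose for subjects who complete Week 24/Visit 6, except for placebo-treated subjects who escape early". SAP 9.6.9 ends exposure at "the date prior to Week 16/Visit 5 for placebo-treated subjects who escape early".

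In SAP 9.6.2, "New events of all TEAEs by exposure interval will be summarized for the Placebo-controlled Phase" in five intervals, the last being everything beyond 12 weeks. The measure is subject incidence. The denominator is the number of subjects whose treatment duration exceeds the interval's lower bound. The Apremilast-exposure version of the table has a cut at 16 weeks; the Placebo-controlled version does not.

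Three provisions bear on the problem:
- SAP 5.5 also defines a Placebo-controlled Phase through Week 16, with its own safety stop dates.
- SAP 9.6.1 gives the exposure-adjusted incidence rate (EAIR) beside subject incidence for adverse events and marked abnormalities, unless otherwise specified.
- SAP 7.2 lists "safety results up to week 24" in the content of the primary analysis.

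**The concern.** A percentage of subjects compares arms fairly only if they are watched for similar lengths of time. In the last interval they are not. A placebo escaper enters the denominator as a full subject and leaves about 4 weeks later. An apremilast escaper, who met the same criterion, stays for about 12 weeks. More placebo escape means less placebo time at risk for the same denominator, so apremilast shows more late-onset events even if the drug causes none.

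Safety and tolerability against placebo is a stated objective, and this table is where a reader would look for late-onset events. Its layout offers no means of separating a drug effect from the escape rule. Stopping placebo escapers' data at the switch is correct in itself, since they then take apremilast. The problem is summarising the resulting unequal time as a crude percentage in one open interval.

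**Working it through.** The plan states no figure for this point, so there is none to reproduce.

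**Inputs**
- Time at risk after Week 12: placebo escapers 16 − 12 = 4 weeks; all other Week 24 completers 24 − 12 = 12 weeks (SAP 5.5, 9.6.1, 9.6.9).
- Denominator: everyone treated for more than 12 weeks (SAP 9.6.2).
- Placebo escape fraction *f*, among those treated beyond 12 weeks: not given for this trial. Assumed range 20% to 50%.
- Equal constant hazard in both arms (no drug effect) and no dropout other than escape.

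**Rare event, interval beyond 12 weeks**

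Mean placebo time at risk = 12(1 − f) + 4f = 12 − 8f weeks, so the crude apremilast/placebo ratio is 12/(12 − 8f). Over the whole phase it is 24/(24 − 8f).

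| f | Placebo weeks after Week 12 | Ratio beyond 12 weeks | Ratio, Weeks 0–24 |
|---|---|---|---|
| 20% | 10.4 | 1.15 | 1.07 |
| 30% | 9.6 | 1.25 | 1.11 |
| 40% | 8.8 | 1.36 | 1.15 |
| 50% | 8.0 | 1.50 | 1.20 |

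**Commoner event**

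Take a 10% risk over 12 weeks. The 4-week risk is 1 − 0.90^(1/3) = 3.45%. At f = 40%, placebo incidence is 0.6 × 10% + 0.4 × 3.45% = 7.4%, against 10.0% on apremilast: ratio 1.36, difference 2.6 percentage points. With a 30% risk over 12 weeks the ratio is 1.14 at f = 20% and 1.46 at f = 50%. The result therefore depends little on how common the event is.

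**A rough anchor for f**

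A footnote to Protocol Table 6, for the ACTIVE study, reports "n with non-missing values were 103 and 91 for Placebo and APR 30 BID at Week 16, and 63 and 76 at Week 24". The placebo fall is (103 − 63)/103 = 39%, which would give 12/(12 − 8 × 0.388) = 1.35. That fall mixes escape with other loss and arose under a different escape rule, so it is only an illustration.

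**Sensitivity of the whole-phase figure to dropout**

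The same footnote shows unequal loss by Week 16: 6 of 109 absent on placebo and 18 of 109 on apremilast. Suppose those absent contributed 8 weeks each, and 40 placebo subjects stopped at Week 16.
- Apremilast: (91 × 24 + 18 × 8)/109 = 21.4 weeks.
- Placebo: (103 × 24 − 40 × 8 + 6 × 8)/109 = 20.2 weeks.
- Ratio: 1.06, against 1.15 without dropout. Assuming 4 or 12 weeks instead of 8 gives 1.04 or 1.08.

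Losses before Week 12 do not enter the denominator of the interval beyond 12 weeks, so they do not offset the artefact there.

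**After the split**

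In an interval from above 12 to 16 weeks, both arms have 4 weeks at risk and the ratio is 1.00. An EAIR for the existing open interval also gives 1.00 under the same assumptions. A small residue remains beyond 16 weeks. The Week 16 visit has a 3-day window (Protocol Table 13) and a target of Day 113 (SAP Table 5). A placebo escaper seen on Day 116 has a last dose on Day 115 and a duration of 115/7 = 16.4 weeks, and so enters that denominator with about 3 days at risk. This is one reason to show a rate there too.

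**The case against.** The strongest reply is that the SAP already provides comparisons with equal planned follow-up. SAP 5.5 defines the phase through Week 16 with safety stop dates, which would have little purpose if no safety analysis used it, and 9.6.1 refers to 5.5. SAP 9.6.2 does not say which phase the interval table uses; on the Week 16 phase, the last interval would in effect be Weeks 12 to 16 and the artefact would vanish. This stands as far as it goes. However, the only data rule spelled out in 9.6.1 is the Week 24 one, so the table would most naturally be run that way.

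A reader might infer that the whole between-arm safety comparison is distorted. The documents do not support that. Planned follow-up is equal to Week 16, the intervals up to 12 weeks are untouched by escape, and EAIR is given by default beside the percentages. The whole-phase ratio is smaller and depends on dropout by arm. SAP 7.2 lists what will be reported through Week 24; it does not make Week 24 the only comparison.

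A reader might also infer that EAIR flatters apremilast for early events, since "Most diarrhea events were of mild or moderate severity and reported within the first 2 weeks of treatment" (Protocol 6.5.5), because late weeks enlarge only the apremilast denominator. That is not so: placebo subjects who do not escape also contribute time to Week 24. Some dilution is possible, but crude incidence through Week 16, the natural measure for such events, is not affected by it.

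Finally, safety is descriptive, and the crude artefact runs against apremilast. Both are true. They limit the consequence without making the interval interpretable.

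**Conclusion.** The point holds for one table. If the new-onset table is run on the phase through Week 24, its open last interval overstates late-onset events on apremilast relative to placebo. For a rare event, the ratio under no drug effect is about 1.15 at 20% escape and 1.50 at 50%. This assumes a constant equal hazard, no other dropout and escape unrelated to adverse-event risk. The escape fraction is an assumption; the direction does not depend on its value.

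For the rest of the safety analysis, the gap is one of wording: 9.6.1 does not say plainly that its summaries are also run through Week 16. The documents give no ground for treating Week 24 safety data as merely supportive, or for dropping crude percentages after Week 16. Placebo subjects remaining after Week 16 are a selected group, so rates there are not a fully randomised comparison. That calls for careful reading of the later data. No test or type I error rate is affected.

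**What to change.** 1. **SAP 9.6.2.** Replace the last Placebo-controlled interval with two: above 12 to 16 weeks, and above 16 weeks. This matches the Week 16 cut in the Apremilast-exposure version. Show EAIR beside subject incidence for the interval above 16 weeks.
2. **SAP 9.6.1.** State that adverse-event incidence, EAIR and shift-to-worst summaries are produced for the phase through Week 16 already defined in 5.5, as well as through Week 24. Keep the Week 24 summaries at their present standing.

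The cost is one more interval, two sentences of SAP text and a repeat run of existing tables with an existing cut-off. No new data are needed.
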